Beyond the above noted issues, the following step will be taken to minimize the likelihood of an adverse reaction to the study: The consent form will clearly describe the nature of the assessments and intervention. Thus, participants who feel uncomfortable with such assessments or intervention programs are not likely to agree to participate.

Potential Benefits. Potential benefits to participants include the use of study phones during the intervention period (at the current time, this benefit is estimated to be unlimited voice and text messages and 2 GB high speed data for the duration of their involvement in the study [i.e., 24 weeks]). Participants may also directly benefit from early detection of and immediate intervention upon presentation of COVID-19 symptoms. Finally, participants may also benefit from the enhanced symptom monitoring that is proposed.

Risks in Relation to Benefits. The current study involves very minimal risk to participants, and the risks of study participation are similar to that of participation in standard care (e.g., loss of confidentiality). All participants will be already seeking standard care before they are provided with any information about the research study. In addition, the knowledge gained from this study may be utilized to improve our understanding of symptom monitoring, health risk factors, and general experiences of individuals who undergo chemotherapy treatments to treat cancer.

We do not anticipate harm to research participants, but the principal investigators will monitor unanticipated problems (including serious and non-serious adverse events) and protocol deviations. Potential unanticipated problems for this project are all non-medical in nature. Unanticipated problems will be submitted within five University business days to the IRB using the Unanticipated Problem Report Form. The following information will be included in an adverse event report: date of event, attribution to data collection, and outcome of adverse events. All adverse events will also be reported in the annual report to the IRB along with a Summary of Participant Harms.

L. Multiple Sites

This is a single-site study.

M. Statistical Methods

Aim 1. We will examine the percentage of prompted daily surveys that are completed throughout the 24-week intervention period and the percentage of participants who report they are satisfied with monitoring and use of mHealth application at the end of the 24-week study period. We will compare participant characteristics (e.g., demographics, health behaviors) and outcomes between those who are satisfied with the app and monitoring versus those who are dissatisfied. We will observe via mHealth app patient health risk factors and readiness to change health risk behaviors in SCC cancer patients. We will compare participant characteristics using chi-square test or independent t-test, as appropriate. The follow-up phone call based qualitative interview (or RedCap interview if a medical condition prevents them from being able to speak for long periods of time) will access participant perceptions of each app feature and be recorded for transcription and analyzed using NVivo. Recordings will be transcribed by internal staff, Microsoft Transcribe, or by approved contractors with whom a Business Associates Agreement has been made. When using Microsoft Transcribe, all transcriptions will be reviewed by study staff. This information will be used to improve this type of symptom monitoring apps in future studies and interventions.

Aim 2. We will examine participant characteristics among those who are and are not transitioned to an Aim 2 monitoring of vital signs and severity of COVID-19 symptoms. We will also examine participant characteristics and outcomes for those that require emergent intervention versus non-emergent intervention. Among those who undergo enhanced monitoring, we will use descriptive statistics to summarize the proportion of patients experiencing the following outcomes: manifestations of severe disease, treatment related toxicity, need for hospitalization, and COVID-19 related mortality. We will also compare outcomes and tolerability of enhanced self-monitoring for severe infection and compare rates of disease related morbidity and mortality to baseline rates published in the literature. We will evaluate participant satisfaction with the app and identify ways to improve this novel patient monitoring technology. We will perform logistic regression to determine the odds of experiencing primary outcomes, based upon baseline characteristics (e.g., sex, race/ethnicity, cancer stage/type). Kaplan-Meier survival curves and log-rank tests of homogeneity will be used to identify the survival functions, describing the time to resolution of symptoms based upon

demographic characteristics. Because COVID-19 is a novel virus and we do not fully understand its impact on our patient population, this study will provide useful, granular information about the daily symptoms of and recovery from COVID-19 in cancer patients.

Aim 3. No analyses proposed, as this is a collaboration aim.

N. Data and Safety Monitoring Plan

Data quality and integrity will be held to the highest standard to ensure accurate reporting and documentation of the objectives outlined in the proposal. The Institutional Review Board and the Office of Clinical Research will monitor data and safety monitoring. The institutional plan for data and safety monitoring for all trials funded by the NCI has been adopted by the University and will be utilized for conduct of our planned proposal.

Procedures to minimize the risk, including of loss of confidentiality, are described in the Protection against Risks section. The study poses minimal risk to participants, therefore the principal investigators (Drs. [name] and [name]) and co-investigators (Drs. [name] and [name]) will undertake continuous monitoring and reporting of events. Although unlikely given our experience, any unanticipated problems will be promptly reported to the IRB. The NIH will be informed of any actions taken by the IRB as a result of its continuing review. Breach of confidentiality is highly unlikely because all data will be encrypted, identified only by numeric code, and/or stored in locked file cabinets/online-secure server. A master list of names and numbers will be kept in a separate location and is used to facilitate the collection of follow-up data. All staff will be fully trained in relevant ethical principles and procedures, particularly around confidentiality.

O. Data Sharing

De-identified summary information about the feasibility of using mHealth technology to assess risk for COVID-19 and interventions to address risk will be shared with the other 2 cancer centers that received CCSG funding on a similar topic. We plan to publish the outcomes of this study and present findings at local and national conferences.

P. Confidentiality

Each participant will be assigned an identification number that will be utilized in place of names in all electronic and print data files. The sheet containing the links between participant names and identifiers will be kept in locked filing cabinet when not in use and will be destroyed 12 months after data collection has been completed. All print information, including informed consent and screening questionnaires, will be stored in a separate locked filing cabinet in the investigators' research offices. All electronic data (with names omitted) will be maintained on the investigators' computers and all computers and electronic files will be encrypted and password protected. When/if the app determines that risk for COVID-19 infection is high, or COVID-19 symptoms are worsening (in those who contract the virus), an encrypted email will be sent from our secure server to clinical study staff that includes the participant name, date of birth and phone number. Participant information will not be released to any party outside the research team at any time.

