The primary objective of this research is to use innovative mHealth technology to monitor symptoms in real-time and facilitate medical triage of high-risk patients. The current study will obtain data on the feasibility of an innovative mHealth application to track symptoms and automatically intervene upon reported high-risk symptoms among cancer patients who are receiving cytotoxic chemotherapy or immunotherapy treatments. This objective will be attained by pursuing the following specific aims:

1. Determine the feasibility, ease of use, and perceived utility of the Symptom Tracker (Insight™) mHealth app to monitor symptoms and health risk behaviors for up to 500 patients who are receiving chemotherapy to treat cancer.
 - a. On average, participants will complete >50% of all prompted daily phone based ecological momentary assessments (EMAs).

- b. Most participants will report that the app is easy to use, and provides useful information (assessed quantitatively and qualitatively during the 24-week phone based or RedCap follow-up interview).
2. Examine participant characteristics and outcomes of those who do and do not test positive for COVID-19 during the 24-week monitoring period.
 - a. Among those who undergo enhanced monitoring, we will use descriptive statistics to summarize the proportion of patients experiencing the following outcomes: manifestations of severe disease, treatment related toxicity, need for hospitalization, and SARS-CoV-2 related mortality.
 - b. We will also compare outcomes and tolerability of enhanced self-monitoring for severe infection and compare rates of disease related morbidity and mortality to baseline rates published in the literature.
 - c. We will use quantitative and qualitative methods to evaluate participant satisfaction with the app among those who test positive for COVID-19 and are asked to report vital signs each day.
3. Collaboratively document and share lessons learned regarding the impact of the COVID-19 pandemic on cancer care delivery via telemedicine and mHealth technology. We commit to a collegial collaboration with other cancer centers funded to study the use of telemedicine through the COVID-19 CCSG supplement mechanism.

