predict study outcomes with less bias than traditional in-person assessments. EMA data will be used to identify and report COVID-19 symptoms to SCC medical staff, assess health risk factors, and collect other health related data that may be used to guide future intervention development with this population. All participants will download the assigned smartphone app to their personal smartphone or receive a smartphone at the baseline visit and will be asked to carry it with them at all times for 24 weeks. Participants will be trained to use the smartphone app for data collection purposes. Participants will be instructed to click the “call staff” button to speak with study research staff in the event that they have difficulty with the phone app. In addition, participants will be instructed that they can click the “Call Clinic Staff” button in the app to speak with medical professionals about their symptoms. In weeks 1-24, participants will be asked to complete one daily survey that will be automatically prompted and administered through an encrypted and secure smartphone app. All participants will be asked to self-initiate a survey (by clicking a button labeled “Report Symptoms” in the app) in the event that any new symptoms arise after the morning survey is completed. Participants will respond to survey questions by using the touch screen.

EMA types. The EMA methodology used in this study will be similar to what has been used in our previous studies, and by other researchers.[24, 25, 28, 30, 39-45] Each EMA will ask about current mood, medication use, perceived social support, pain, and symptoms consistent with COVID-19. This daily survey will take approximately 2 minutes to complete (see Table 1 and Appendix). Every Monday, participants will complete additional items focused on health risk factors, depression, anxiety, and medication use. The phone will ring and vibrate to cue these EMAs for 30 seconds. If the participant has not responded after 5 prompts, the EMA will be recorded as missed. Participants may also initiate a survey by clicking a Report Symptoms button in the app when COVID-19 symptoms arise later in the day (see Table 1 and Appendix). All EMAs will be date and time stamped for future analyses.

Table 1: Study Measures

MEASURE	ITE MS	FULL BATTERY ASSESSMENTS			Chart Revie w	EMA ASSESSMENTS
		Scree n	Bas e	24- W		
Descriptive Variables						
Screening Questionnaire	11	X				Sleep

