All participants will be prompted to complete EMAs once per day during the 24-week study time period. If a participant contracts COVID-19, they will click the “COVID-19 Positive” button in the app. This action will cause the app to ask a different set of questions focused on enhanced monitoring COVID-19 symptoms for the next 21 days. At the end of 21 days, the app will return to daily prompts of the pre-COVID-19 EMAs. At the conclusion of the 24-week EMA period, participants will gain access to a new button in the app that will initiate the 24-week follow-up assessment (see Appendix). Participants will receive a daily alert from the app to click the “Final Survey” button in the app to complete the end of study assessment. The 24-week phone interview (or RedCap interview if a medical condition prevents them from being able to speak for long periods of time) will be scheduled at the baseline visit and the date/time of the call will appear at the top of the app home screen. A maximum of five phone call/text attempts and one mailed letter will occur over two-week period, before data from phone interview (or RedCap interview if a medical condition prevents them from being able to speak for long periods of time) will be considered unattainable. Those participants who were loaned a mobile phone to use during the study will be mailed a stamped envelope to return the phone and charger, or will be approached by study staff to reclaim the mobile device during a routine follow-up visit in the SCC chemo infusion clinic. Upon receipt of the smartphone and charging equipment, all equipment will be sterilized with alcohol-based sanitizer in accordance with current practice guidelines put forth by the Centers for Disease Control at the time it is returned by the study subject.

EMA completion rates, participant dropout, and feedback on the participant satisfaction survey will be used to evaluate feasibility of this type of mobile intervention in this population.

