When participants provide a pattern of responses that are suggestive of heightened risk for COVID-19 (See algorithm in Appendix), they will receive a suggestion to contact SCC staff, and the app will send an encrypted email containing this information to [name] and other SCC staff with a request to contact the participant to assess symptoms (see Appendix) and whether urgent medical attention is indicated. Should urgent medical attention be warranted, the patient will be instructed to the clinical unit most appropriate to the symptoms they reported through the app algorithm or discussed with the clinical nursing or physician staff. Non-emergent patients who screen positive for COVID-19 will begin an enhanced symptom and vital sign monitoring period that will continue until the participant reports that they are no longer symptomatic and/or a medical professional informs them that they no longer need to self-quarantine, which is expected to be approximately 21 days. These patients will receive a pulse oximeter (provided by the study) and the app questions will change to include daily prompts requesting that the patient input morning vital signs (temperature, heart rate, blood oxygen levels (SpO2)) and answer questions specific to the severity of symptoms and/or emergence of new symptoms of COVID-19. If a patient is hospitalized, they can continue to complete the daily assessments if they are willing and able to do so. The app will also support check-ins with SCC staff and after-hours medical staff as needed after diagnosis of COVID-19 or until the patient has been medically released from self-quarantine. Once the participants have completed the enhanced symptom and vital sign monitoring portion of the study, the pulse oximeter will be returned to the research team at the time of their next scheduled appointment. These devices will then be sterilized with both alcohol-based sanitizing products as well as ultraviolet light exposure in accordance with practices endorsed by the Centers for Disease Control.

Participants will continue to use the app to complete a final 24-week follow-up survey and will be contacted by phone (or RedCap if a medical condition prevents them from being able to speak for long periods of time) to complete a brief qualitative interview 24 weeks after study enrollment. Relevant demographic, cancer-specific and COVID-19 related data will be extracted

from electronic health records at the conclusion of the study.

E. Chart Review

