Study staff will conduct a chart review on OUHSC campus computers using OU Medicine's electronic medical record. Chart review will be conducted after completion of the EMA period. Initial evaluation, treatment plan, and follow-up notes will be searched for the following data points:

- a) Cancer Stage at Initial Presentation
- b) Type of Cancer – text field
- c) History of Previous Cancer Diagnosis
- d) Previous Cancer Treatment
- e) History of Previous Cancer Treatment with Surgery
- f) History of Previous Cancer Treatment with Chemotherapy
- g) History of Previous Cancer Treatment with Endocrine Therapy
- h) History of Previous Cancer Treatment with Radiation
- i) History of Previous Other Types of Cancer Treatment
- j) Receiving concurrent chemotherapy and radiation
- k) Body Mass Index at start of treatment
- l) Body Mass index at end of treatment
- m) Number of no-show and cancelled office visits
- n) Referral to Supportive Care
- o) Distance in miles from the participant's home to the SCC?
- p) Does the participant reside in a rural county?

All data collected during the chart review will be assigned to the corresponding participant ID number and entered into study electronic databases in accordance with the data and safety-monitoring plan outlined below. See Appendix for a full list of data that will be collected via chart review.

F. Biospecimens

No biospecimens will be collected as part of this study.

G. Banking/Repository/Database

No biospecimens will be banked for future use. All data will be stored and accessed on OUHSC devices/computers.

H. Inclusion / Exclusion Criteria

Individuals will be included in the study if they:

- 1) Demonstrate > 6th grade English literacy level (i.e., phone based EMAs require >6th grade literacy)
- 2) Present for care at the Stephenson Cancer Center at the University of Oklahoma Health Sciences Center
- 3) Are currently receiving cytotoxic chemotherapy or immunotherapy by intravenous infusion or by orally delivered medication
- 4) Are greater than or equal to 18 years of age
- 5) Are willing and able to complete surveys on their personal smartphone or a study provided smartphone
- 6) Are willing and able to provide informed consent

There are no early termination criteria; however, individuals can elect to stop participation in

mobile app monitoring at any time.

I. Gender/Minority/Pediatric Inclusion for Research

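### Does the >50% completion target fail because the plan does not say how to count days after a participant stops app monitoring?

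*Combined protocol and SAP*

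**What the plan says.** The target is in Section A, Aim 1a: "On average, participants will complete >50% of all prompted daily phone based ecological momentary assessments (EMAs"). Section M, Aim 1, gives the matching analysis: "We will examine the percentage of prompted daily surveys that are completed throughout the 24-week intervention period". Both are worded in terms of prompted surveys.

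Three statements in Section D bear on the denominator:
- The schedule: "All participants will be prompted to complete EMAs once per day during the 24-week study time period".
- The rule for non-response, under EMA types: "If the participant has not responded after 5 prompts, the EMA will be recorded as missed".
- The feasibility measures: "EMA completion rates, participant dropout, and feedback on the participant satisfaction survey will be used to evaluate feasibility".

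Section H deals with leaving: "There are no early termination criteria; however, individuals can elect to stop participation in" app monitoring whenever they choose. It does not say whether prompting then ends or how the remaining days are counted. Section M attaches no test, interval or decision rule to the 50% figure.

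**The concern.** A participant who keeps the app but stops answering is still prompted, and each unanswered survey is recorded as missed. A participant who formally withdraws may no longer be prompted. On a strict reading of prompted, that person's remaining days then leave the denominator. The same loss of monitoring could therefore lower the completion figure in one case and leave it untouched in the other.

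This is the only percentage target for the primary aim, since Aim 1b asks only for a majority. The data are also meant to support a later funding application (end of Section A). If the denominator is chosen after the data are seen, the more favorable figure could be the one reported.

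**Working it through.** There is no plan figure to reproduce. The >50% is a target, and the documents give no derivation for it and no expected dropout rate.

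**Inputs from the protocol**
- Scheduled surveys per participant: 24 × 7 = 168 (Section D).
- Completion in the team's similar studies: 82% to 87% (Section D, Smartphone training).

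**Inputs assumed**
- Completion while active, c, where it differs from 82% to 87%.
- Share of participants stopping, d.
- Day of stopping, t.
- Leavers and stayers have the same c while active.

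**Formulas**
- Completion of prompted surveys, if prompting ends at withdrawal: c.
- Completion of scheduled days, with later days counted as missed: c × (1 − d + d × t/168).
- Share stopping at which the scheduled-day figure falls to 50%: d = (1 − 0.5/c) / (1 − t/168).

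**Size of the difference**

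| c | d | t | Of prompted | Of scheduled days |
|---|---|---|---|---|
| 60% | 30% | 56 | 60.0% | 0.60 × (0.7 + 0.3 × 56/168) = 0.60 × 0.80 = 48.0% |
| 60% | 10% | 56 | 60.0% | 0.60 × (0.9 + 0.1 × 56/168) = 56.0% |
| 82% | 30% | 56 | 82.0% | 0.82 × 0.80 = 65.6% |

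Only the first row changes whether the target is met.

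In that row, suppose a share s of leavers withdraws and the rest fall silent. The participant mean is then 0.42 + 0.3 × (0.6s + 0.2(1 − s)) = 0.48 + 0.12s. It passes 50% when s exceeds 0.02/0.12 = 17%, which is 0.3 × 0.167 = 5% of all participants. When completion is modest, the way people leave therefore does matter.

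**Share that must leave to change the verdict, for exit at day 14 and at day 84**

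| c | Exit at day 14 | Exit at day 84 |
|---|---|---|
| 55% | 10% | 18% |
| 60% | 18% | 33% |
| 70% | 31% | 57% |
| 82% | 0.390/0.917 = 43% | 0.390/0.5 = 78% |
| 87% | 0.425/0.917 = 46% | 0.425/0.5 = 85% |

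**What the text already supports.** The daily schedule applies to all participants, the analysis covers the whole 24 weeks, and silence is recorded as missed. Read together, these point to 168 for everyone. The prompted-only reading needs a further premise, that prompting ends on withdrawal, which no section supplied states.

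**What a reader could recover.** The scheduled-day figure needs only the number of completed surveys divided by 168. The prompted figure needs the record of completed and missed surveys. Section D says surveys are date and time stamped, so both are available. In the first row, 60.0% of prompted surveys reported beside 30% dropout at day 56 leads directly to 0.60 × 0.80 = 48.0%.

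**The case for a change.** The strongest case for a change is that the schedule describes what the app is set to do and never mentions people who stop. An analyst could defend either denominator once the results are known. Dropout is named as a measure but has no definition, threshold or link to the 50% target, so reporting it does not by itself settle whether Aim 1a was met. Nor do the earlier rates guarantee a wide margin. The 87% in Section C came from a three-week intervention, whereas this study asks patients on cancer treatment for 24 weeks of unpaid daily surveys. Even with no change of verdict, the 82% example moves the reported figure by 82.0 − 65.6 = 16.4 points. A few sentences would remove the doubt.

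Much of this stands as description. The rule is not written, 82% to 87% is not a forecast for this population, and a choice made after seeing the data would be undesirable. It does not show that the plan as written misleads. Every change of verdict shown rests on assumed inputs that the documents do not support. Completion while active, with dropout reported separately, is also a legitimate way to present feasibility, and it keeps apart two different reasons for missing data. Folding both into one scheduled-day figure is a different choice of measure, on which reasonable statisticians differ.

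**Conclusion.** The gap is real but small, and the plan need not change. No section supplied says how days after a voluntary stop are counted. The surrounding text leans towards the fixed 168-day count, and dropout is to be considered beside completion on either reading. The target carries no test and no go/no-go rule, and both versions of the figure can be computed at the end of the study.

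At 82% to 87% completion, the verdict on >50% changes only if about 43% to 85% of participants leave between days 14 and 84. At an assumed 60% it changes with 18% to 33%. The judgment therefore rests partly on completion while active staying well above the target, which the earlier studies suggest but do not establish for 24 weeks. If completion proved modest, the report would still be interpretable with both denominators and the dropout count in view. This is a missing detail that analysts can fill, together with a fair trade-off between two measures.

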Qualitative interview data. A qualitative interview will be conducted at the end of the 24-week study period via a brief phone call (or RedCap if a medical condition prevents them from being able to speak for long periods of time). This interview will assess opinions about the app, ways the app could be improved for future patient monitoring, etc. The follow-up phone call will be recorded for transcription and analyzed using NVivo. Recordings will be transcribed by internal staff, Microsoft Transcribe, or by approved contractors with whom a Business Associates Agreement has been made. When using Microsoft Transcribe, all transcriptions will be reviewed by study staff. De-identified information will be shared with collaborators and colleagues at other NCI Designated Cancer Centers (see Aim 3).

Data from the electronic health record. Relevant data from the EHR will be extracted as needed to address any discrepancies or omissions surrounding specified study outcomes that have been collected through the smartphone EMA surveys. This supplemental information will be collected and stored in REDcap.

Private identifiable data (e.g., participant names, study assessment dates, and contact information) will be required for participant contact and thus will be collected in this study. Private identifiable data will be used to contact participants and will be saved in compliance with university storage of PHI (e.g., encryption). All printed private identifiable data will be stored in a locked filing cabinet in [name] research office when not in use and will be destroyed 12 months after data collection is completed.

Smartphone programming. The mHealth Shared Resource at the OUHSC and Stephenson Cancer Center (SCC) has developed the Insight™ mHealth Platform that empowers researchers to build, test, and launch technology-based assessment and intervention tools. The mHealth resource employs a program manager, four senior programmers, and two research technicians, who develop and maintain web and mobile applications and relational databases. Applications are developed using state-of-the-art cross-platform design tools. The Resource is located within the Oklahoma Tobacco Research Center (OTRC), where [name] office is located. [name] is the Scientific Director of the mHealth Shared Resource, which will provide the programming services for the proposed project.

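### The dedicated app ratings available for Aim 2c fall at week 24, up to 21 weeks after enhanced COVID-19 monitoring ends, and no rating is tied to that phase

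*Combined protocol and SAP*

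**What the plan says.** Section A, Aim 2c, undertakes to "evaluate participant satisfaction with the app among those who test positive for COVID-19 and are asked to report vital signs each day", by both qualitative and quantitative means. The pieces that determine when this is measured are spread over Sections D and M.

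- **Follow-up.** Section D, after Table 1: "All participants will be prompted to complete EMAs once per day during the 24-week study time period".
- **Enhanced monitoring.** The same paragraph says that a positive report makes the app "ask a different set of questions focused on enhanced monitoring COVID-19 symptoms for the next 21 days". It continues: "At the end of 21 days, the app will return to daily prompts of the pre-COVID-19 EMAs". The Study application text in Section D gives a different end: resolution of symptoms and/or release from quarantine, "which is expected to be approximately 21 days".
- **Dedicated ratings.** Table 1 marks the App Quality Questions (3 items) and the Treatment Improvement Interview (13 items) in the 24-W column and in no other. Section D, Qualitative interview data: "A qualitative interview will be conducted at the end of the 24-week study period via a brief phone call". The Study application text likewise has participants "complete a brief qualitative interview 24 weeks after study enrollment". Section M, Aim 1, takes the percentage who say they are "satisfied with monitoring and use of mHealth application at the end of the 24-week study period".
- **Another app rating.** As far as the layout can be read, the EMA column of Table 1 lists an app evaluation beneath its Weekly EMA heading, with no item count. The EMA types paragraph, which describes the Monday items, does not name it.
- **Aim 2 analysis.** Section M, Aim 2, says that satisfaction will be evaluated, without an instrument, a time point or a reference period.

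**The concern.** The participants of interest in Aim 2c spend about three weeks on a special version of the app and then go back to the routine one. The instruments built to rate the app reach them at week 24, whenever the infection occurred. Someone infected early is asked to look back over months of routine surveys.

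Two things are at stake. The first is recall: Section D justifies EMA on the ground that it captures experience as it happens and with less bias, yet the rating of the enhanced phase is left to memory. The second is attrition: a participant who completes enhanced monitoring and then dies, or cannot be reached at week 24, contributes no dedicated rating, although one could have been obtained when the phase ended. The results are meant to support a later funding application and fully powered trials, so the acceptability of the enhanced component is worth measuring well.

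**Working it through.** The plan states no lag, sample size or precision for Aim 2c, so there is no figure to reproduce. The check is on timing.

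**Inputs**
- Follow-up: 24 weeks = 168 days (Section D).
- Enhanced period: 21 days, fixed in one place and approximate in the other (Section D).
- Dedicated ratings: week 24 (Table 1; Section D; Section M, Aim 1).
- Contact attempts for the interview: up to two weeks (Section D).
- Day *t* of the positive report: not given. Taken as uniform over 0 to 168 for illustration (assumption).

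**Formula.** Lag from the end of enhanced monitoring to week 24 = max(0, 168 − 21 − *t*) = max(0, 147 − *t*) days.

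**Results**
- Maximum, *t* = 0: 147 days = 21 weeks. With the two-week contact window for the interview: 161 days = 23 weeks.
- Mean under uniform onset: 147² / (2 × 168) = 21,609 / 336 = 64.3 days = 9.2 weeks.
- Median: 147 − 84 = 63 days = 9.0 weeks.
- Lag over 4 weeks: (147 − 28) / 168 = 70.8%.
- Lag over 12 weeks: (147 − 84) / 168 = 37.5%.
- Lag over 20 weeks: (147 − 140) / 168 = 4.2%.
- Still in enhanced monitoring at week 24, so with no lag: 21 / 168 = 12.5%.

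**Sensitivity to onset.** If all positive reports came in the first 4 weeks, lags would run from 147 − 28 = 119 days (17 weeks) to 21 weeks. If all came in the last 8 weeks (*t* of 112 or more), no lag would exceed 147 − 112 = 35 days (5 weeks).

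**Sensitivity to the length of the phase.** Because the two descriptions of its end differ, the maximum was also computed for other lengths: 14 days gives 154 / 7 = 22 weeks, 28 days gives 140 / 7 = 20 weeks, and 42 days gives 126 / 7 = 18 weeks. The conclusion does not turn on this.

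**The weekly item.** If the weekly app evaluation stayed active, it would fall on 21 / 7 = 3 Mondays within a 21-day phase. If it were suspended and resumed with the routine surveys, the next Monday would come within 7 days. The plan does not say which applies, and nowhere assigns the item to Aim 2c.

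**The case against.** The strongest reply is that the plan may already hold what is needed.

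- **Weekly app evaluation.** Table 1 appears to schedule it, so a reader who infers that satisfaction is measured at week 24 and at no other time goes further than the documents allow. This stands. What it leaves open is whether the item is shown during the enhanced phase and whether it is meant for Aim 2c.
- **What is rated.** Aim 2c names satisfaction with the app, and the vital-sign clause defines the subgroup. A whole-app rating within that subgroup fits the wording. This stands, but such a rating still looks back over a gap of weeks for most onset dates.
- **Separability.** A reader might infer that week-24 answers cannot distinguish the enhanced module from the routine app, since routine days make up 147 / 168 = 87.5% of follow-up for someone with one full enhanced period. The documents do not support that. Share of days is not weight in a rating, the interview is to cover each app feature (Section M, Aim 1), and the COVID-19 Positive button is a listed feature (Section D, Smartphone training). The appendix items, which would show wording and branching, are not available.
- **Stopping the app.** Section H lets people stop app monitoring, and nothing bars interviewing them afterwards. The interview is scheduled at baseline, with repeated contact attempts and a RedCap alternative. Stopping app use alone therefore does not remove the week-24 interview.
- **Other evidence.** Survey completion is time-stamped, so adherence during the enhanced phase can be observed. It is useful, but it is not a satisfaction rating.

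**Conclusion.** The point holds as a gap in measurement and specification, with an inexpensive improvement available. The dedicated instruments come at week 24, the lag is at most 21 weeks and about 9 weeks on average under uniform onset, and no rating is tied to the enhanced phase. The maximum and the placement of the instruments come from the documents. The average, and the 12.5% still in the phase at week 24, rest on the uniform-onset assumption and would move with the local epidemic.

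Two further inferences should not be drawn. Section B cites mortality of up to 20% in infected cancer patients, and a reader might take this as the share of Aim 2c ratings lost. The figure is for cancer patients in general, whereas enhanced monitoring begins in non-emergent patients, so it need not apply to this group. Nor do the documents show that late ratings would favour the enhanced component; the direction of any bias is unknown.

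Aim 2c is a descriptive secondary aim in a feasibility study, and the primary aim is unaffected. The change is worth making because it reduces recall and attrition problems for a named aim at little cost.

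**What to change.** 1. Show the three existing App Quality Questions in the app when enhanced monitoring ends, worded to refer to daily vital-sign reporting. Offer them also if a participant stops using the app during that phase.
2. As an alternative or an addition, keep the weekly app evaluation active during enhanced monitoring, and say so in Table 1 and in the EMA types paragraph.
3. In Section M, Aim 2, name these ratings as the quantitative measure for Aim 2c, with their time point and reference period. Keep the week-24 interview as the qualitative part.
4. Reconcile the two descriptions in Section D of when enhanced monitoring ends, so that the trigger for the prompt is defined.

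The cost is a small amendment, minor app programming and one extra short prompt during recovery. The end-of-phase prompt does not recover ratings from participants who die during enhanced monitoring; it does secure them from those who complete the phase and later die or cannot be reached.
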